Since there are no safety data for the medications to be evaluated on all arms of this study in the mild to moderate SARS-CoV-2 infected population, the first six patients on each arm will be evaluated for any grade 3 or higher hematologic or non-hematologic toxicity for 14 days. Patients coming off study before the first 14 days for reasons other than toxicity will be replaced. If two or more of the six patients in this arm of the study develop unacceptable toxicity, the treatment for that arm would be considered unsafe and stopped. Patients exhibiting rapid progression of COVID-19 symptomatology requiring intensive care hospitalization or intubation will come off study and will be considered failures in terms as per the primary endpoints of the study but nor for safety and will be replaced if these cases occurred during the phase 1 portion of the study.

Once the phase 1 portion safety run-in has concluded, that arm will be opened for phase II accrual.

Patients will be assigned to each arm in cohorts of three at a time until accrual numbers for each arm are fulfilled or discontinued due to safety concerns occurring beyond the Phase 1 portion. Monthly phone conferences among investigators during enrollment will take place.

Patients will undergo baseline mobile EKG or standard EKG to evaluate QTc interval on Day 1 (or within 5 days of registration if inpatient) and a repeat EKG at Day 14 (+/-4 days). Any Chest X-ray or CT scan of the chest that is performed for routine care will be reviewed by the PI for eligibility and recorded on case report forms. NOTE: if a patient develops a myocardial infarction or grade 3 or 4 cardiac arrhythmia while on the 14 days of drug, they should be immediately taken off study medication and receive standard of care treatment per their treating physician.

Patients will be followed for clinical outcomes by phone contact each week and hospitalizations, and all complications will be recorded on adverse event case report forms.

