## **6.2 Definition of Dose-Limiting Toxicity (DLT) for phase I run in portions of this protocol**

A DLT is defined as any of the below treatment emergent toxicities with attribution of definitely, probably or possibly related to one or more of the study drugs that occur during the first 14 days of study treatment. Toxicities that occur after the 14 day treatment period will be reported through adverse event reporting outlined in section 10.0, but will not be counted as DLTs.

- **Grade 3 or higher non-hematologic or non-hematologic toxicity at least possibly, probably or definitely related to study medication or procedures, per DMID Toxicity Scale for Determining Severity of Adverse Events**

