#### **Less common known potential toxicities, 1% - 10%:**

Thrombocytopenia

Hypokalemia

Liver function abnormalities

Jaundice

Itching or skin eruption/rash

Nephrolithiasis

Diabetic ketoacidosis

Abdominal pain or bloating

Pancreatitis

Pregnancy: There is insufficient evidence to prove safety of camostat mesilate in pregnant females.

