## 9. STATISTICAL CONSIDERATIONS

### 9.1 Study Design/Endpoints

This study is a randomized, multi-arm phase II trial. No proven effective therapies currently exist for COVID19 (Sanders J et al. JAMA April 13, 2020), thus a selection design using the frequentist pick-the-winner design will be employed as early screening for promising therapies. The primary objective is to rapidly evaluate multiple potential inhibitors of SARS-CoV-2 viral replication in COVID19 positive patients with high-risk factors in order to decrease clinical deterioration, defined as a less than 2 point decrease in initial COVID 7-POINT ORDINAL OUTCOMES SCALE within 14 days from study entry (primary). As an example, if a person enters the study at ORDINAL SCALE 6 and does not worsen to 4 or less, that is considered a success.

For each arm a phase I lead in portion, six patients per group will be followed in order to evaluate dose limiting toxicities and preliminary safety. If 2 of the first 5 patients or if  $\geq 2$  of 6 patients experience DLT, the regimen will not be considered safe for further evaluation.

The trial will be powered based on the primary endpoint of the rate of patients who will exhibit less than 2 levels of decrease in COVID 7-POINT ORDINAL SCALE from baseline to Day 14. The goal of selection designs is to select with high probability should a superior treatment exist. Note that hypothesis testing or comparisons between arms or with a placebo is not performed with this design and subsequent trials are needed for definitive hypothesis testing of the promising arm.

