### **SERIOUS OR LIFE-THREATENING AEs**

ANY clinical event deemed by the clinician to be serious or life-threatening should be considered a grade 4 event. Clinical events considered to be serious or life-threatening include, but are not limited to seizures, coma, tetany, diabetic ketoacidosis, disseminated intravascular coagulation, diffuse petechiae, paralysis, acute psychosis, severe depression.

HEMATOLOGY				
	Grade 1	Grade 2	Grade 3	Grade 4
Hemoglobin	9.5-10.5 g/dL	8.0-9.4 g/dL	6.5-7.9 g/dL	<6.5 g/dL
Absolute Neutrophil Count	1000-1500/mm 	750-999/mm 	500-749/mm 	<500/mm 
Platelets	75,000-99,999/mm 	50,000-74,999/mm 	20,000-49,999/mm 	<20,000/mm 
WBCs	>13,000/mm 	13,000-15,000/mm 	15,000-30,000/mm 	>30,000 or <1,000/mm 
Polymorphonuclear Leucocytes + Band Cells	>80%	90-95%	>95%	-----
Abnormal Fibrinogen	Low: 100-200 mg/dL High: 400-600 mg/dL	Low: <100 mg/dL High: >600 mg/dL	Low: <50 mg/dL -----	Fibrinogen associated with gross bleeding or with disseminated coagulation
Fibrin Split Product	20-40 µg/mL	41-50 µg/mL	51-60 µg/mL	>60 µg/mL
Prothrombin Time (PT)	1.01-1.25 × ULN	1.26-1.5 × ULN	1.51-3.0 × ULN	>3 × ULN
Activated Partial Thromboplastin (APPT)	1.01-1.66 × ULN	1.67-2.33 × ULN	2.34-3 × ULN	>3 × ULN
Methemoglobin	5.0-9.9%	10.0-14.9%	15.0-19.9%	>20.0%

CHEMISTRIES				
	Grade 1	Grade 2	Grade 3	Grade 4
Hyponatraemia	130-135 mEq/L	123-129 mEq/L	116-122 mEq/L	< 116 mEq/L or abnormal sodium with mental status changes or seizures
Hypernatraemia	146-150 mEq/L	151-157 mEq/L	158-165 mEq/L	> 165 mEq/L or abnormal sodium with mental status changes or seizures
Hypokalaemia	3.0 - 3.4 mEq/L	2.5 - 2.9 mEq/L	2.0 - 2.4 mEq/L or intensive replacement therapy or hospitalization required	< 2.0 mEq/L or abnormal potassium with paresis, ileus or life-threatening arrhythmia
Hyperkalaemia	5.6 - 6.0 mEq/L	6.1 - 6.5 mEq/L	6.6 - 7.0 mEq/L	> 7.0 mEq/L or abnormal potassium with life-threatening arrhythmia
Hypoglycaemia	55-64 mg/dL	40-54 mg/dL	30-39 mg/dL	<30 mg/dL or abnormal glucose with mental status changes or coma
Hyperglycaemia (non-fasting and no prior diabetes)	116 - 160 mg/dL	161- 250 mg/dL	251 - 500 mg/dL	> 500 mg/dL or abnormal glucose with ketoacidosis or seizures
Hypocalcaemia (corrected for albumin)	8.4 - 7.8 mg/dL	7.7 - 7.0 mg/dL	6.9 - 6.1 mg/dL	< 6.1 mg/dL or abnormal calcium with life threatening arrhythmia or tetany

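### The DLT definition behind the 2-of-6 run-in stop names non-hematologic toxicity twice and, read literally, leaves out drug-related grade 3 or higher cytopenias

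*Combined protocol and SAP*

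**What the plan says.** Four parts of the combined protocol and SAP bear on the run-in decision.

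- **Section 6.2** restricts DLTs to the toxicities listed under its lead sentence. They must be at least possibly "related to one or more of the study drugs that occur during the first 14 days of study treatment". One bullet follows: "Grade 3 or higher non-hematologic or non-hematologic toxicity at least possibly, probably or definitely related to study medication or procedures", graded on the DMID scale.
- **Section 9.1** makes DLT the trigger. If 2 of the first 5, or at least 2 of 6, "patients experience DLT, the regimen will not be considered safe for further evaluation".
- **Section 6.1** describes the same run-in in other words: "the first six patients on each arm will be evaluated for any grade 3 or higher hematologic or non-hematologic toxicity for 14 days". Its stop then reads "If two or more of the six patients in this arm of the study develop unacceptable toxicity", in which case the arm is treated as unsafe and closed. It defines no such term and sets no attribution condition. It also provides that patients with "rapid progression of COVID-19 symptomatology requiring intensive care hospitalization or intubation will come off study"; they count as efficacy failures but not as safety events, and are replaced.
- **Section 8.1** lists expected toxicities by drug, without grades. Artesunate (Arm F) has neutropenia and anemia above 10%. Camostat (Arm D) has "Thrombocytopenia" at 1% to 10%. Ivermectin (Arm C) and *Artemisia annua* (Arm E) have no cytopenia listed.

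The Hematology table in Appendix G grades these events, with rows for hemoglobin, "Absolute Neutrophil Count" and platelets among others.

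**The concern.** The defect lies in the rule that decides whether an arm opens to phase II. Section 6.2 is the only place where DLT is defined, and 9.1 counts nothing but DLTs. With hematologic toxicity missing from the definition, two drug-related grade 3 or 4 cytopenias in an arm's first six patients would not meet the stop as written.

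Section 6.1 points to a broader scope but does not settle the matter, because its trigger is a different, undefined term. The two versions also differ on attribution: 6.2 and 9.1 require at least a possible relation to treatment, and 6.1 requires none. Someone applying 6.1 alone could count an unrelated event. Someone applying 6.2 alone could pass over a related cytopenia.

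Section 6.1 gives the lack of safety data in this population as the reason for the run-in, so what it counts should be beyond argument.

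**Working it through.** The plan states no operating characteristic for the run-in, so there is no figure to reproduce. The check is a comparison of texts, a count of what is affected, and one illustration on assumed rates.

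**Step 1. The same decision in three places**

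| | Section 6.1 | Section 6.2 | Section 9.1 |
|---|---|---|---|
| Term for the trigger | Unacceptable toxicity, not defined | DLT, defined | DLT, as in 6.2 |
| Hematologic grade 3+ | Named in what is evaluated | Not named | Inherits 6.2 |
| Non-hematologic grade 3+ | Named | Named twice | Inherits 6.2 |
| Attribution | None stated | At least possibly related | Inherits 6.2 |
| Threshold | 2 or more of 6 | None stated | 2 of first 5, or 2 or more of 6 |

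The thresholds agree, since 2 of the first 5 already implies at least 2 of 6. Scope and attribution do not agree.

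**Step 2. A worked case.** Suppose two of six artesunate patients have a drug-related neutrophil count below 500/mm³, which is grade 4 in Appendix G, and nothing else occurs.

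- 6.2 as written: 0 DLTs of 6, so the arm opens to phase II.
- 6.2 with hematologic toxicity included: 2 DLTs of 6, so the arm stops.

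**Step 3. What is in scope**

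- Arms with a cytopenia listed in 8.1: D and F, 2 of 4, with three terms (thrombocytopenia, neutropenia, anemia).
- Planned run-in patients, not counting replacements: 6 × 4 = 24 in all; 6 × 2 = 12 in arms D and F.
- Hematology rows in Appendix G: hemoglobin, neutrophils, platelets, white cells, polymorphonuclear leucocytes plus bands, fibrinogen, fibrin split product, PT, APTT and methemoglobin. That is 10 rows, all with a grade 3 entry (for example hemoglobin 6.5–7.9 g/dL, neutrophils 500–749/mm³, platelets 20,000–49,999/mm³). Under the literal wording none of the 10 can give a DLT.

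**Step 4. Direction of the effect, on assumed rates only.** The documents give no grade 3 or higher rates. Assume a per-patient drug-related rate *a* of 5% or 10% for non-hematologic toxicity and *h* from 0% to 30% for hematologic toxicity, independent of each other. The probability of stopping at 2 or more of 6 is

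P = 1 − (1 − p)⁶ − 6p(1 − p)⁵,

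with p = a under the literal definition and p = 1 − (1 − a)(1 − h) when both kinds count. For a = 5% and h = 20%, p = 1 − 0.95 × 0.80 = 0.24 and P = 0.442, against 0.033 with p = 0.05.

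| Assumed h | a = 5%: literal | a = 5%: both counted | a = 10%: literal | a = 10%: both counted |
|---|---|---|---|---|
| 0% | 3.3% | 3.3% | 11.4% | 11.4% |
| 5% | 3.3% | 10.9% | 11.4% | 21.2% |
| 10% | 3.3% | 21.2% | 11.4% | 32.0% |
| 20% | 3.3% | 44.2% | 11.4% | 53.6% |
| 30% | 3.3% | 65.2% | 11.4% | 71.7% |

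Under the literal wording the stop does not respond to hematologic toxicity at any rate. The table shows that property; it is not an estimate for any arm.

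**The case against.** The best defence is that 6.1 already answers the question. It names both kinds of toxicity and goes on, in the same paragraph, to say that two or more patients with unacceptable toxicity close the arm. The natural antecedent is the toxicity just named. On that reading two grade 3 cytopenias stop the arm whatever 6.2 says, and the doubled word is a slip that staff would see through.

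That reading is plausible, and it is good evidence of intent. It does not make the rule consistent: the 6.1 term is undefined and lacks the attribution condition, and 9.1 names DLT as the trigger. Nor is a non-hematologic-only reading absurd within this protocol. Sections 1.2.5 and 12.2 define severe adverse events for a secondary objective in non-hematologic terms, so a reader could take 6.2 as deliberate.

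Other points on that side stand in part:

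- **Safeguards.** During the run-in, Section 10.3 sends drug-related events of grades 1 to 5 to the PI, IRB and monitoring committee in expedited fashion, and under 13.3 that committee can suspend or terminate the trial. Two such events would not go unseen. This softens the consequence, but discretionary review does not replace the prespecified count.
- **The count of 10 rows.** Not all are cytopenias, and fibrinogen, fibrin split product, PT, APTT and methemoglobin are not in the safety laboratory tests of the study calendar. The count shows how far the definition reaches, not how many events to expect.
- **Timing of the blood count.** The Day 14 sample may fall up to 4 days late, outside the 14-day DLT window. That is a separate point, which the wording change does not address.

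**Conclusion.** The concern holds. As written, the only DLT definition omits hematologic toxicity, and 9.1 closes an arm on that definition, so drug-related grade 3 or higher cytopenias do not count toward the stop. The slip is almost certainly unintended, and its consequence is softened by reporting and committee oversight. It nevertheless sits in an operative safety rule and should be corrected.

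The size can be stated only as scope: 2 of 4 arms have cytopenias listed in 8.1, and they hold 12 of the 24 planned run-in patients. No probability of wrongly opening or closing an arm is claimed, because the 8.1 listings carry no grades and the documents give no grade 3 or higher rates. The conclusion rests on the wording of 6.1, 6.2 and 9.1, and not on the illustrative rates.

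**What to change.** Two phrases change.

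1. In 6.2, replace the bullet's scope with: *any hematologic or non-hematologic toxicity of grade 3 or above that is at least possibly related to study drug*. This drops the reference to procedures, in line with the section's lead sentence, which speaks only of study drugs. The sponsor may keep that reference without affecting the point.
2. In 6.1, replace *unacceptable toxicity* with *a DLT as defined in Section 6.2*, and keep the existing exemption for rapid COVID-19 progression to intensive care or intubation. This also removes the attribution mismatch. Section 10.4 points the same way by exempting unrelated COVID-19 events, but it governs reporting and not the run-in count, so 6.1 should say so itself.

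The cost is the text change alone. The two-of-six threshold, the sample size and the visit schedule are unaffected, and a blood count with differential and platelets is already in the study calendar at Day 1 and Day 14 (±4 days).

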## **6.3 Duration of Therapy**

In the absence of treatment delays due to adverse event(s), treatment is given until one of the following criteria applies:

- Intercurrent illness that prevents further administration of treatment
- Unacceptable adverse event(s)
- Patient decides to withdraw from the study
- General or specific changes in the patient's condition render the patient unacceptable for further treatment in the judgment of the investigator
- Patient non-compliance
- Pregnancy
- The drug manufacturer can no longer provide the study agent
- Admission to the Intensive Care Unit and/or need for mechanical ventilation. At this

time, the treating physician will have the ability to continue study drug, discontinue therapy, place the patient on another study trial, or treat the patient with alternative therapies, per their clinical judgement. At this point, the patient will be followed by the study team to track outcomes and monitor for adverse events that might be attributable to study drug but the drug will be considered to have failed the primary endpoint

The reason(s) for protocol therapy discontinuation, the reason(s) for study removal, and the corresponding dates must be documented in the Case Report Form (CRF). For clarity, “off treatment” is the date when all medication has been completed (including the normal observation period) or discontinued due to one of the factors above, and no further treatment is planned. This is the date the patient has been officially taken off treatment. “Off study” is the date after which no further follow-up of the patient will occur

#### **6.4 Duration of Follow-Up**

Patients will be followed for up to 40 days from the beginning of therapy or until death, whichever occurs first.

### **7. DOSING DELAYS/DOSE MODIFICATIONS**

N/A.

### **8. PHARMACEUTICAL INFORMATION**

A list of the adverse events and potential risks associated with the investigational or commercial agents administered in this study can be found in Section 10.1.

#### **8.1 Drug Ordering and Accountability**

##### *8.1.1 Procurement of medications:*

Prescriptions for medications will be written by the site PI, qualified Co-I (physician), or treating physician as outlined in Section 6.0. IDS will order and dispense ivermectin, camostat mesilate, artesunate and other investigational agents if new arms are opened during the treatment phase of this trial. Drug accountability will be maintained on a National Cancer Institute Drug Accountability Report Form (DARF). Artemisia annua, a natural product/botanical, will be ordered directly from Baesman Distributors.

##### *8.1.2 Storage & Drug Accountability:*

The University of Kentucky Investigational Drug Service pharmacist will ensure that all study drug is stored in a secured, limited access storage area, under recommended storage conditions in accordance with applicable labeling and regulatory requirements and as provided by the separate study drug accountability manual. Under no circumstances should the investigator or other site personnel supply study drug to other investigators, patients, or clinics. Adequate records documenting receipts, use, return, loss, or other disposition of study provided drugs must be kept. The University of Kentucky Investigational Drug Service will supply drug accountability forms that will be used, or may approve use of standard institution forms. Drug accountability

and supply order instructions and forms will be provided in a separate study manual. The accountability ledgers will be maintained to contain current and accurate inventory records and must be readily available for inspection. Unless otherwise authorized by the sponsor, at the end of the clinical trial all drug supplies unallocated or unused by sites or patients must be returned to the University of Kentucky Investigational Drug Service (UK IDS) for final actions in accordance with sponsor instructions.

The exception to this practice will be the natural product, Artemisia annua tea or coffee which is commercially available and will be supplied by Artemilife, via its distributor, Baesman distributors (see Appendix H for instructions)

### 8.1.3 Ivermectin

#### Procurement

This medication will be dispensed by IDS service.

#### Formulation

3mg tablets

#### Preparation, Storage and Stability

Please refer to package insert for complete preparation and dispensing instructions.

Dispense eight 3mg tablets (for patients < 75 kg); ten 3 mg tablets (for patients  $\geq$  75 kg)

#### Administration

Refer to the treatment section 6.1 for specific administration instructions.

Patients should be instructed to take: 4 tabs on Days 1 and 2, (12 mg total daily dose) for weight < 75 mg; or 5 tabs on Days 1 and 2, (15 mg total daily dose) for weight  $\geq$  75 kg. Ivermectin should be taken on an empty stomach.

#### Drug Interactions

Increased Effect/Toxicity: CYP3A4 and ABCB1 inhibitors may increase therapeutic concentrations of ivermectin, avoid concurrent use of ivermectin and strong CYP3A4 or ABCB1 inhibitors

Decreased Effect: Ivermectin may decrease the therapeutic effect of BCG and live vaccines, avoid concurrent use

Herb/Nutraceutical Interactions: None

#### Pharmacokinetics

Absorption: Well absorbed, administer on empty stomach. High fat meal increased bioavailability 2.5 fold

Distribution: Vd: 3.1-2.5 L/kg, does not cross blood brain barrier

Metabolism: Hepatic via CYP3A4 (major)

Half-life elimination:

Terminal: 18 hours

Excretion: Less than 1% via feces and urine

#### Adverse Events

Consult the package insert for the most current and complete information.

**Common known potential toxicities, > 10%:** None

**Less common known potential toxicities, 1% - 10%:**

Tachycardia (4%)

Peripheral edema (3%)

Dizziness (3%)

Diarrhea (2%)

Eosinophilia (3%)

Elevations in LFTs (2%)

**Rare known potential toxicities, <1% (Limited to important or life-threatening):**

Hyperbilirubinemia

Hypersensitivity

Pregnancy: There is insufficient evidence to prove safety. Based on the animal and human data ivermectin is labeled category C in the US (animal EFD finding, but only at doses also toxic to the pregnant female). The manufacturer considers it contraindicated in pregnancy.

#### 8.1.4 Camostat Mesilate

#### Procurement

This medication will be dispensed by IDS service.

#### Formulation

100 mg tablets

#### Preparation, Storage and Stability

Tablets should be stored at room temperature.

Dispense 84, 100 mg tablets

#### Administration

Refer to the treatment section for specific administration instructions

Patients should be instructed to take two 100 mg tablet, three times per day (after meal) Days 1-14.

#### Drug Interactions

Increased Effect/Toxicity: No known drug interactions

Decreased Effect: No known drug interactions

Herb/Nutraceutical Interactions: No known drug interactions

### Pharmacokinetics

Absorption: well absorbed orally

Distribution: Not established

Metabolism: Metabolized to two major metabolites: the carboxylic acid derived from cleavage of the carboxamide (FOY-251); and the carboxylic acid derived from cleavage of the internal carboxyester (GBA). Both are rapidly eliminated with elimination half-lives of roughly 1 hour. FOY-251 retains activity against the protease target.

Half-life elimination: 170 minutes

Terminal: Not reported

Excretion: Most of the substance is excreted by 5 to 6 hours after dosing, through all routes including fecal, urine, bile, etc. About 20% of a 200 mg dose is excreted into the urine as GBA and about 1% is excreted as FOY-251

### Adverse Events

#### **Common known potential toxicities, > 10%:**

None reported

#### **Less common known potential toxicities, 1% - 10%:**

Thrombocytopenia

Hypokalemia

Liver function abnormalities

Jaundice

Itching or skin eruption/rash

Nephrolithiasis

Diabetic ketoacidosis

Abdominal pain or bloating

Pancreatitis

Pregnancy: There is insufficient evidence to prove safety of camostat mesilate in pregnant females.

